6.4.7 Study termination

The sponsor reserves the right to modify or terminate the study at any time. Possible reasons for termination are:

- Safety reasons – the incidence of AEs in this or any other study using the same treatment regimen indicates a potential health risk for the participants.
- New scientific knowledge becomes known that makes the objectives of the study no longer feasible/valid.
- Unsatisfactory enrolment of participants.
- Regulatory requirement.
- Drug manufacturing/stability issues.
- Force majeure events.

6.4.8 Study Treatment Discontinuation

The primary reason for study treatment discontinuation will be documented as extensively as possible. Subjects who discontinue study treatment prematurely will be followed-up until the end of study, or until they withdraw consent.

6.5 Treatment Drug

The treatment drug will be prescribed as an IMP to study participants and dispensed by a registered UK pharmacist. The treatment drug will be labelled in English and packaged in accordance with the regulations that apply to dispensed relevant medicinal products (in accordance with the requirements of Schedule 5 to the Medicines for Human Use (SI 1994/3194) Regulations 1994).

6.5.1 Treatments administered

The treatment regimen will be as follows; a vaporised/inhaled medical cannabis strain (CBMP), namely Equipose 8-8 with a balanced 8% THC and 8% CBD content. Treatment is a full spectrum medical cannabis product presented as dried flower:

The cannabis will be delivered by a smart vaporiser device manufactured by Ryah. This is CE marked having passed CE-RED NB and IEC 60601 medical device safety tests. It is a temperature-controlled vaporiser with flow sensors that connects remotely with a smart-device. hosted application which collects dosing data from the vaporiser and patient reported outcomes, permitting further dosing only after completion of required data entry. The CBMP is placed in a prefilled cartridge which contains 250 mg of product. This cartridge is QR coded and must be read by the mobile application prior to loading into the vaporiser. Detailed instructions on how to use the vaporiser will be provided with each vaporiser and a UK-based technical helpline will be provided in case the subject needs to be assisted with vaporiser use.

Treatment is determined by the study Physicians based on the subject's medical history, their subtype of chronic pain and their experience with CBMP use. Study Physician will be given extensive guidance on state of the art of CBMP prescribing, ensuring that subjects can tolerate the CBMP and are not given a dose of THC that might cause excessive adverse events. All subjects will be prescribed an initial low dose of CBMP. Real-time evaluation of efficacy and tolerability will allow dose to be titrated appropriately.

Using the principles of universal precaution all subjects will start the protocol at a low dose. At the low dose the subject will commence with one 1 vape session (250 mg of cannabis) in the evening only. All subjects will progress to the higher dose at 1 month after baseline, unless

instructed not to by the study clinician, who will review how well the subject has tolerated the CBMP. The higher dose will consist of 2 vape sessions (250 mg total cannabis flos per cartridge) one in the morning and one in the evening.

6.5.2 Selection of doses in the study:

A considerable body of clinical studies support the use of medicinal cannabis in chronic non-cancer pain. The optimal treatment for chronic pain is achieved by dosing carefully with titration to achieve the required pharmacological effects. The study clinician will closely monitor the dosage during the treatment of the participant. Titrating if necessary, to improve response to treatment and ensure the treatment is well tolerated.

6.5.3 Treatment compliance

Treatment compliance will be monitored by regular and prompted ePRO interactions via the study mobile phone application and by contacting the subjects directly to discuss the progress of medication protocol. These contacts will be recorded in the subject record under "Documents" in the medical management database used for this study "Heydoc". Due to the self-funded aspect of the study and the nature of the condition being treated, good trial protocol compliance is expected.

In addition, at each quarterly review, study clinicians will ask the subjects about their medicine taking experience and their compliance and they will also note this in the subject record under "Consultations" in the medical management database used for this study "Heydoc".

6.5.4 Contraindicated Medicines

After oral intake, THC is mainly metabolized in the liver by cytochrome P450 (CYP) 2C9, 2C19 and 3A4 to much more psychoactive 11-hydroxy- Δ^9 -THC and inactive 11-nor-9-carboxy- Δ^9 -THC (Abraham et al., 2007). Cannabinoids are weak inhibitors of cytochrome P450 (CYP). Δ^9 -THC inhibits CYP3A4, 3A5, 2C9 and 2C19. CBD inhibits CYP2C19, 3A4 and 3A5, although this can be observed only at doses higher than clinically used. Nevertheless, caution is advised with concomitant fentanyl and amitriptyline use, as both are metabolized through CYP3A4, and 2C19 (Sativex product monograph). Most drug interactions are an effect of the concurrent use of other agents' depression of the central nervous system. Clinically significant interactions are rare, and cannabis may be combined safely with many medications (McCallum and Russo, 2018).

6.5.5 Treatment after end of study

Subjects will be free to continue to receive treatment and medical care at the clinic after termination of the study, in compliance with local regulations. Those not receiving ongoing treatment at the clinic, no further follow up or data will be collected on these subjects. Any data from patients who continue to receive treatment after the 3-year study period will be outside the study and will not contribute to the study database.

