6.4.3 Contraceptive Guidance

The safety and tolerability of medicinal cannabis has been studied and the adverse event and safety profile is well understood. The use of CBMP is not advisable during pregnancy, therefore we will ask for provision of evidence of a negative pregnancy test for women of child-bearing age, before treatment can commence. Evidence of a negative pregnancy test for women of child-bearing age (section 3.1 for definition) needs to be provided at screening and 3 months after the completion of the treatment period. It is mandated that males and females of a child bearing age use an acceptable barrier methods of contraception (see section 3.1 for definition) is used during the duration of the study (irrespective of whether the participant is using a hormonal contraceptive) from screening throughout the study and for 3 months after the last dose of the study treatment. The effectiveness of systemically acting hormonal contraceptives may be reduced by CBMP, therefore female participants using systemically acting hormonal contraceptives must add an additional second barrier method.

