7.1 Definitions

An **adverse event** is any untoward medical occurrence in a participant who has been administered a cannabis product and which does not necessarily have a causal relationship with this treatment. An adverse event (AE) can therefore be any unfavourable and unintended sign (including an abnormal laboratory finding), symptom, or disease temporally associated with the use of a medicinal product, whether related to the medicinal product.

Adverse events will be graded with respect to intensity and classified as either serious or non-serious according to the World Health Organisation classification.

Classification of adverse events

Intensity	Mild	Some awareness of symptoms, but easily tolerated.
	Moderate	Symptoms causing enough discomfort to interfere with usual activity.
	Severe	Incapacitating event causing inability to work or to perform usual activity.
Seriousness	Serious	Any untoward medical occurrence that at any dose: 
 - results in death - is life-threatening - requires participant hospitalisation or prolongation of existing hospitalisation - results in persistent or significant disability/incapacity - is a congenital anomaly / birth defect - is an important medical event.
	Non-serious:	Any other adverse event.

Note: The term "life-threatening" implies only the fact that the participant was at immediate risk of death. The term "life-threatening" does not imply a possible future course which might or might not have happened but was prevented due to adequate physician's action. For example: A simple bacterial wound infection can lead to gangrene, sepsis and eventually to death; while sepsis is usually regarded as a Serious Adverse Event because of the known high mortality, the primary wound infection itself is usually not regarded as a Serious Adverse Event. In analogy, a newly diagnosed malignant disease is usually regarded as a Serious Adverse Event because malignant diseases usually have a high mortality rate and are, therefore, life-threatening.

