7.2 Assessment and reporting of adverse events

The occurrence of adverse events will be assessed by non-directive questioning of the participant at each visit. Further, adverse events volunteered by the participant during or between visits or detected through observation, physical examination, laboratory test, or other assessments during the observation period, will be documented. Participants will be instructed that they must immediately report any adverse events, subjective complaints or objective changes in their well-being to the study doctor or the clinic personnel, regardless of the perceived relationship between event and test product.

All AEs will be recorded by the study doctor or clinic personnel in the CRF and subject notes from the signing of informed consent until the end of the trial (3 years of treatment). The AEs will be followed until resolved, if applicable.

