7.3 Reporting of serious adverse events

All serious adverse events (SAEs) are to be recorded in the CRF and subject's notes from the signing of informed consent until the end of the trial (after 3 years of treatment).

SAEs must be reported immediately to the sponsor. The study doctors or clinic staff are required to notify the sponsor by completing the Serious Adverse Event template and emailing or faxing the sponsor, within 24 hours of them becoming aware of the occurrence of a serious adverse event. The sponsor is responsible for notification to the appropriate authorities, if applicable (A serious adverse event reporting form template must be prepared and made available to the investigators for quick reporting).

All SAEs should be reported promptly to the REC, if applicable in accordance with the International Conference on Harmonisation Good Clinical Practice (ICH GCP) E6, (Section 4.11.1). The SAE will then be followed until resolved, if applicable.

If the SAE was unexpected, it is then defined as a Suspected Unexpected Serious Adverse Reaction (SUSAR) and should be reported by the sponsor to the MHRA and relevant REC. If the SUSAR is fatal or life threatening, then these should be reported immediately and at least not later than seven days after the sponsor was first aware of the reaction. Any additional relevant

information should be sent within eight days of the report. Electronic reporting will be adopted using the MHRA's eSUSAR website, the EudraVigilance Gateway or EVWEB. The sponsor shall keep detailed records of all adverse events relating to the clinical trial which are reported to it by the study doctors or clinic staff for the trial. The Licensing Authority may require the sponsor to send those records, or copies of such records, to the authority. For all other SUSARs the sponsor must inform the MHRA and relevant REC within 15 working days of them becoming aware of the SUSAR.

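### Appendix 1 stops all data collection at the end of study, yet requires a pregnancy test three months after treatment and follow-up of adverse events to resolution

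*Protocol*

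**What the plan says.** All of the text at issue is in Appendix 1, the draft CANPAIN protocol.

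- **Length of treatment.** Section 3.1 (Definitions of terms) limits each participant's trial to 3 years, and 6.1 has treatment continue to the end of the study.
- **Recording window.** Section 7.2 records AEs "from the signing of informed consent until the end of the trial (3 years of treatment"). Section 7.3 records SAEs "from the signing of informed consent until the end of the trial (after 3 years of treatment").
- **After the end of study.** Section 6.5.5 says of people who leave the clinic: "Those not receiving ongoing treatment at the clinic, no further follow up or data will be collected on these subjects". Data from those who go on with treatment "will be outside the study and will not contribute to the study database". No exception is stated.
- **Pregnancy.** Under 6.4.3, evidence of a negative test "needs to be provided at screening and 3 months after the completion of the treatment period", and contraception applies "from screening throughout the study and for 3 months after the last dose of the study treatment". Pregnancy is a listed reason for stopping study drug (6.4.4). An event that "is a congenital anomaly / birth defect" is an SAE (7.1).
- **Open events.** Section 7.2 adds: "The AEs will be followed until resolved, if applicable". Section 7.3 says the same of SAEs. Section 7.4 continues examinations until the condition resolves or the study doctor judges them unnecessary.
- **Early discontinuation.** Section 6.4.8 keeps people who stop treatment early in follow-up until the end of study or withdrawal of consent.

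**The concern.** The protocol itself sets a safety window that runs 3 months past the last dose. For anyone treated to the end of the 3 years, that window lies wholly after the point at which 6.5.5 ends data collection. A result is demanded and then given no place to be recorded.

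The same clause collides with the duty to follow open events to resolution. At the end of study, site staff would have one section telling them to carry on and another telling them that nothing more is collected.

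At stake is how complete the safety record is at its far end: the late test result, pregnancies and births that become known after closure, and the outcomes of events still open. Completers carry the 3-year pain comparison in 9.5.1.1, so this is not a marginal group.

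**Working it through.** The protocol gives no figure to reproduce, and no power or event count is involved. The check sets the stated time windows side by side.

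**Someone treated for the full 3 years**

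| Item | Source (Appendix 1) | Month |
|---|---|---|
| Last dose in the study | 3.1, 6.1 | 36 |
| End of AE and SAE recording | 7.2, 7.3 | 36 |
| Data collection ends (leavers), or data fall outside the database (continuers) | 6.5.5 | 36 |
| Pregnancy test due, contraception requirement ends | 6.4.3 | 36 + 3 = 39 |
| Follow-up of open events ends | 7.2 to 7.4 | when resolved, no calendar limit |

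The test falls 3 months after closure whether the person leaves the clinic or stays. A leaver has no data collected. A continuer's data do not count.

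**Someone who stops at month t**

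The test is due at t + 3, and 6.4.8 keeps the person in follow-up to month 36. The test lies inside the study when t + 3 ≤ 36, that is, t ≤ 33. The gap therefore concerns completers and people who stop after about month 33.

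**Is there a contact for the test?**

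Table 1-1, as far as it can be read, has a baseline column, daily, weekly and monthly collection, and 3-monthly follow-up visits. It shows no pregnancy-test row and no post-treatment column. The table may be incomplete in the available text, so it is not enough alone. The prose schedule in 6.6.1 agrees with it: Day 0, daily, weekly and 3-monthly items, with no pregnancy test and nothing after treatment.

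**Pregnancies near closure**

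A birth before the end of study can be reported under 7.1 to 7.3. A pregnancy or birth that first becomes known after closure is outside the SAE recording window and outside 6.5.5. Section 6.4.4 lists pregnancy separately from AEs, so it is unclear whether the follow-to-resolution duty would reach an ongoing pregnancy.

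**Which end of study?**

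The table uses 3 years per participant. Section 6.1 also places the end of the study after the last subject's 3 years, and 8.1 refers to a date five years after entry. The number of people affected depends on which of these governs.

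**The case against.** The strongest reply is that the safety sections already do most of the work. Sections 7.2 to 7.4 separate recording new events (to the end of trial) from following recorded ones (to resolution). Those specific duties could be read as overriding the general statement in 6.5.5, whose heading confines it to the time after the study. On that reading, events open at month 36 are not lost and only a clarifying phrase is needed. This is a fair reading, but 6.5.5 contains no exception that says so. For open events the accurate statement is therefore that the instructions conflict, not that outcomes are certainly discarded. The reply does not help the month-39 test, because no section provides for collecting it.

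A reader might also infer three stronger things that the protocol does not support:

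- **That safety collection closes when treatment stops, for everyone.** Section 6.4.8 rules this out: early discontinuers stay in follow-up to the end of study.
- **That pregnancies and birth defects could never be reported.** Participants must report AEs at once and are asked at each visit (7.2), medical history is updated every 3 months (6.1), and a birth defect arising before closure is an SAE.
- **That the missed pregnancies can be counted.** The protocol does not give the number of women of childbearing potential. Its failure rate above 1% per year, in 3.1, describes certain methods taken singly, whereas 6.4.3 has hormonal users add a barrier method. No defensible lower bound follows.

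Finally, all of this is in an appended draft of a later trial. That stands as a limit on urgency. It does not remove the point: section 2 of the feasibility protocol takes its treatment and tests from Appendix 1 and says that CANPAIN will be submitted again.

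**Conclusion.** The point holds in limited form. For completers and those who stop after about month 33, Appendix 1 requires a test result about 3 months after the last dose and gives it no contact and no place in the database. Pregnancies or births first known after closure are in the same position. For events still open at closure, 6.5.5 and 7.2 to 7.4 give incompatible instructions.

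The size is a window of up to 3 months per affected participant, plus an open-ended period for unresolved events. No count of affected people is offered, because the protocol does not supply the inputs.

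The conclusion assumes that the end of study means 3 years for each participant and that Table 1-1 lacks no relevant row; section 6.6.1 supports the second. The gap at month 36 cannot arise within the 3-month feasibility period. The absence of pregnancy tests between screening and the late test is not part of this finding, and nothing is said here about how often to test or what contraception to require.

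**What to change.** Reconcile 6.4.3, 6.5.5 and 7.2 to 7.4 before CANPAIN is resubmitted:

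1. In 6.5.5, except three things from the bar on further follow-up: the 3-month post-treatment contact, AEs and SAEs unresolved at closure, and the outcome of pregnancies already exposed to study treatment. State that these data belong to the study database whether or not the person stays at the clinic.
2. In 7.2 and 7.3, align the recording window with the 3-month point that 6.4.3 already sets.
3. In Table 1-1, and correspondingly in 6.6.1, show that contact and the test that 6.4.3 already requires.
4. Use a single definition of the end of study in 3.1, 6.1 and 8.1, so that closure has one date.

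The cost is amendment wording, one remote contact at a time when a result is already required, and later closure of the safety database. No new test, testing frequency or clinical rule is proposed.

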6.6 Assessments and schedule of measurements (overview)

The following assessments and measurements will be carried out at the times specified in the schedule of assessments (Table 1-1).

Informed consent will be obtained prior to any study-related procedures.

6.6.1 Assessments during the study

- **Initiation visit/call (Day 0)**

Day 0 (baseline) for each subject will be the initial clinic visit when treatment is started. Alongside the daily monitoring of CBMP tolerability through the patient reported outcomes,

subjects will have 3 monthly consultations..

- Complete medical questionnaire form
- Review of medical history and relevant investigations
- Review current treatment being received or proposed
- Assess inclusion and exclusion criteria
- Written informed consent obtained
- Discuss the medicinal cannabis therapy
- Go through dosing instructions with participants (i.e., how to use the device, when to use the CBMP and how to enter data onto their smart device).
- If appropriate arrange the prescription

Daily assessments (concomitant with dosing)

- Tolerability NRS measurements (anxiety, drowsiness, dizziness, shortness of breath)

The tolerability measures collected 30 minutes after dosing with the CBMP are collected and fed back to Heydoc. Any NRS score >5 causes an alert, which triggers a study physician to contact the subject to assess their status and to elicit an appropriate response.

Weekly assessments

- Efficacy NRS measurements (pain, well-being, sleep quality, fatigue, nausea, depression, appetite)
- Global impression of change

3 monthly assessments

- Quality of life (SF-12)

3 monthly visits/call

- Review of efficacy and tolerability of medicinal cannabis and establishing the subject's overall impression on how they have responded to the CBMP
- Review current treatment being received or proposed
- Adverse events
- Renew prescriptions. Remind the participants of dosing instructions

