The inhaled route of delivery is the most controllable and predictable route of delivery for the administration of CBMPs. Heating a 250 mg sachet of CBMP in the medical grade vaporisers produces vapor which contains consistent quantities of active phytochemicals, is quickly absorbed with rapid onset of action. The rapid kinetics allow a faster dose titration, enabling the correct dose to be achieved while minimising side effects. Importantly, vaporised CBMP produces blood levels of active ingredients, principally THC and CBD, with a relatively short duration of activity (up to 1 hour), which reduces the risk of a long-lasting side effects, of importance if the subject receives an accidental overdose. This is a distinct advantage over other routes of delivery such as oral and sublingual which have substantially longer durations of activity (6 to 8 hours).

Table 1) List of eight major cannabinoids found in medical cannabis in their active decarboxylated forms

Name (abbreviation)	Structure
(-)-trans- Δ^9 -tetrahydrocannabinol (THC)	
Cannabidiol (CBD)	
CBG	
CBN	
CBC	
THCV	
CBDV	
CBGV	

In cannabis, alongside cannabinoids, there are 11 major terpenes (α -pinene, β -pinene, β -myrcene, limonene, terpinolene, linalool, α -terpineol, β -caryophyllene, α -humulene, and caryophyllene oxide) (Ibrahim et al., 2019). It is thought these compounds in various concentrations interact with cannabinoids to produce the variety of medicinal effects found in the cannabis strains used by medicinal cannabis patients (Russo, 2011), through the entourage effect.

There are strains that produce high levels of THC and low levels of CBD, strains that have the opposite profile and strains that are balanced. The medical cannabis community describe products in terms of their THC and CBD content:

- 1) High THC (>10 %) / low CBD (<3 %)
- 2) Mid THC / mid CBD (balanced THC to CBD, at approximately 10 %)
- 3) Low THC (<3 %) / high CBD (>10 %).

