data will trigger automatic alerts to clinicians who will contact those subjects for assessment. Subjects will have quarterly consultations with specialists to discuss their treatment and to collect adverse events, until the end of the 3 years of treatment. On each 3 monthly follow up, an updated medical history will be taken, alongside information on current standard of care treatment and a review of the CBMP prescribed will be undertaken (see figure 1).

Under the supervision of an appropriately qualified and trained physician, all subjects will be prescribed a dose of CBMP product that is appropriate for their type of chronic non-cancer pain, their medical history and their previous experience with cannabis. Cannabis tolerance will be monitored via ePRO data collection with tolerability questions asked after each vapourisation session. After 1 month of treatment at the low dose, this information will be used, alongside regular monitoring of the subject, to guide the Investigator on whether the subject can be titrated to the higher dose. The length of the trial for each participant is 3 years. Treatment will continue until the end of the study (see figure 1). An overview on the study procedures is given in the schedule of assessments (Table 1-1).

Figure 1; schematic of patient journey

Stage 4	
Clinic treatment phase
 
Predominantly application-based data collection, video consultation/face-to-face reviews at 3-month timepoints. Review tolerability, treatment effects and concomitant changes to standard of care
 
Patients asked if they want to join CANPAIN study and are provided with PIS about study and draft study consent form.
 
If they want to enter study inclusion/exclusion criteria confirmed and meeting arranged to review study consent form and get it signed.
 
Study protocol followed for this patient from this point on until end of maximum of 3 years

---------	--

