6.2 Discussion of study design and choice of control groups

The aim of the study is to evaluate whether the addition of medical cannabis to standard of care or at the completion of standard of care is beneficial with regards to pain scores, quality of life, quality of sleep and changes in the use of concomitant medication, as well as being safe and tolerable in subjects suffering from chronic non-cancer pain. The study will utilise a combination of patient reported outcomes and data from the NHS (chronic pain diagnosis, standard of care and health related laboratory tests) to provide a holistic evaluation of the CBMP treatment when combined with standard of care. The patient reported outcomes and NHS data will be transferred into an electronic health repository which will manage their day to day care, provide reports and alerts on the tolerability of the cannabis for each subject and will form the clinical trial database. The matched controls will exclude those potential participants who are consuming illicit cannabis, identified by drug screening. If participants are using illicit cannabis, they will be given the option to stop with a 3-week wash out period. If participants are not willing to cease, they will not be eligible for inclusion in the matched control cohort.

Controls

The analyses of effectiveness will be conducted through comparison with matched controls obtained from NHS sites established to enable data collection from consented subjects receiving standard of care only. Subjects who consent to have their data collected will be asked to provide essential demographic information, details on their chronic pain type, their standard of care and whether they are currently using medical cannabis to help with their pain. This information will be used to match the subject to subjects on the trial. The data collected in the match cohort will mirror the data collected from the CANPAIN minus tolerability data which will not be required.

The CANPAIN study will follow a pragmatic, real-world, 'all-comers' design with wide inclusion criteria, which is designed to result in a more representative sample of the target population and of the matched controls. Baseline characteristics of treated participants may still differ systematically from those of the matched control group and one must account for these systematic differences when estimating the effect of treatment on outcomes.

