6.7 Effectiveness, tolerability and safety measurements

6.7.1 Effectiveness measurements

Change from baseline in pain intensity (pain NRS).

Change from baseline in quality of life measure (SF-12)

Change from baseline in well-being (well-being NRS)

Change from baseline in fatigue (fatigue NRS)

Change from baseline in nausea (nausea NRS)

Change from baseline in depression (depression NRS)
Change from baseline in anxiety (anxiety NRS)
Change from baseline in appetite (appetite NRS)
Change from baseline in sleep quality (sleep NRS)
Change from baseline in use of concomitant pain medications
Patient's global impression of change (PGIC)

Generally, these quarterly reports compare the results to the previous quarterly results and the Specialist can make comments about the changes from the previous period.

Numerical data will be collated and reports made on the baseline changes for pain, QoL, well-being, fatigue, nausea, depression, appetite, sleep quality, anxiety, global impression of change and concomitant medication, to define whether the subject has received benefit.

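### Anxiety is counted as an effectiveness change from baseline, but the only scores scheduled are taken 30 minutes after a dose, with no pre-dose baseline

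*Protocol*

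**What the plan says.** All references are to the CANPAIN protocol in Appendix 1 unless stated.

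- **Endpoint.** The synopsis lists anxiety NRS under effectiveness, among the secondary variables. Section 6.7.1 lists "Change from baseline in anxiety (anxiety NRS") and says that reports on the changes will cover, among others, "appetite, sleep quality, anxiety, global impression of change and concomitant medication, to define whether the subject has received benefit". Section 9.5.1.1 plans descriptive statistics for anxiety changes.
- **Weekly efficacy schedule (6.6.1).** "Efficacy NRS measurements (pain, well-being, sleep quality, fatigue, nausea, depression, appetite"). Anxiety is not in the list.
- **Daily schedule (6.6.1), tied to dosing.** "Tolerability NRS measurements (anxiety, drowsiness, dizziness, shortness of breath"). On timing: "The tolerability measures collected 30 minutes after dosing with the CBMP are collected and fed back to Heydoc". Section 6.1 agrees: "tolerability questions asked after each vapourisation session".
- **Baseline.** The Day 0 list in 6.6.1 names no anxiety score. Table 1-1 marks neither the additional efficacy assessments nor the intolerance assessments at Day 0. In the feasibility protocol, section 2 names only pain and quality-of-life questionnaires before the first dose. Section 6.2 says all analyses use changes from baseline.
- **Pharmacology (4.1).** Vaporised product acts "with a relatively short duration of activity (up to 1 hour"). The inhaled peak is at about 10 minutes and the initial half-life is 1 to 2 hours. Anxiety is named as an acute adverse effect of THC.
- **After stopping treatment.** Section 6.4.8 keeps subjects in follow-up to the end of the study unless they withdraw consent.
- **Controls (6.2).** The control data mirror the treated data "minus tolerability data which will not be required". The synopsis states that the secondary variables cannot be compared with the matched controls.

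**The concern.** The same scale serves two purposes that need different timing. As a tolerability signal, a score shortly after inhalation is what one wants. As a measure of whether treatment has changed the patient's anxiety, it needs a score that is not tied to a dose, and a baseline taken on the same footing. The schedule supplies only the first kind.

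If the protocol is followed as written, a patient who is briefly calmed by each dose could be reported as having improved anxiety. A patient made briefly anxious by each dose could be reported as worse. In neither case would the report show whether anxiety between doses had changed. The result would still feed the statement on whether the subject benefited. A later analysis plan cannot repair this, because it cannot recover scores that were never scheduled.

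**Working it through.** **1. Endpoint list against schedule.** Section 6.7.1 has eight NRS effectiveness scales: pain, well-being, fatigue, nausea, depression, anxiety, appetite and sleep. The weekly list in 6.6.1 has seven of these. Anxiety is the one left out, and its only named place in 6.6.1 is the daily post-dose set.

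**2. Is 30 minutes inside the acute window?** Inputs, all from section 4.1: peak at about 10 minutes; activity up to 1 hour; initial half-life 60 to 120 minutes. The scoring time of 30 minutes is from 6.6.1.

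- Share of the stated activity period elapsed: 30/60 = 50%.
- Time since peak: 30 − 10 = 20 minutes.
- Fraction of peak remaining, assuming simple exponential decline from the peak: 0.5^(20 / half-life).
  - Half-life 60 minutes: 0.5^(20/60) = 0.79.
  - Half-life 120 minutes: 0.5^(20/120) = 0.89.

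On either figure, the scheduled score is taken while the drug is acting.

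**3. What the change would measure.** Write observed change = lasting change + acute effect at 30 minutes. There is one observed quantity and there are two unknowns. Illustrative values in NRS points:

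| Lasting change | Acute effect | Observed change |
|---|---|---|
| −1 | 0 | −1 |
| −2 | +1 | −1 |
| 0 | −1 | −1 |

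These three different situations give the same reported result.

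**4. Which baseline?** None is scheduled. A Day 0 score on its own would not be enough: it would be an undosed reading set against dosed ones, so the two terms in step 3 would stay combined. If the first post-dose score served as baseline instead, it would already contain drug effect.

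**5. After dosing stops.** The daily set is triggered by a session. With no session there is no scheduled score. Section 6.4.8 continues follow-up and section 9.3 analyses all recruited subjects whether or not the regimen was followed, yet for anxiety the schedule supplies nothing after discontinuation.

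No sample size or power figure in the protocol bears on this point.

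**The case against.** **Anxiety is mainly a tolerability outcome here.** The synopsis objectives name it only in connection with tolerability, and for that purpose, and for the alert in 6.6.1, the 30-minute score is suitable. This stands. It means that removing anxiety from the effectiveness lists is as valid a repair as adding a weekly score. It does not make the present combination workable.

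**Table 1-1 may cover it.** The table has an unitemised weekly row for additional efficacy assessments, an overall efficacy and tolerability assessment weekly and at three-monthly visits, and an intolerance row also marked at those visits. None excludes an anxiety score, but none names one, and 6.6.1 itemises the weekly scales without it. The likeliest explanation is an omission from the list. The text still has to be corrected, because the ePRO would be built from it.

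**Stronger readings that the documents do not support.**

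- A reader might infer that the absence of control scores is a hidden flaw. It is disclosed: the synopsis disclaims comparison for secondary variables, section 9.5.1.1 makes any such comparison conditional on similar data in both databases, and the control-compared secondary objective in section 5 does not name anxiety.
- A reader might infer that the score measures acute effect alone. It contains underlying anxiety as well; the problem is that the two cannot be separated.
- A reader might take the activity of up to 1 hour and conclude that the scores represent only 1 to 2 of 24 hours. The half-life in the same section does not allow so sharp a cut-off: at 1 hour, 0.5^(50/60) = 56% to 0.5^(50/120) = 75% of peak would remain.
- A reader might infer that patients made anxious by dosing drop out and tilt the result towards benefit. That is possible, but no figure in the protocol gives its direction or size. What can be said is that the score is not scheduled after stopping.

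**Conclusion.** The point holds as an inconsistency between the effectiveness list and the assessment schedule, with a real consequence for interpretation. As scheduled, the change from baseline in anxiety has no defined baseline, mixes lasting and acute effects inseparably, and stops when dosing stops.

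The effect is limited. Anxiety is one of several secondary variables, its analysis is descriptive, and it belongs to the Appendix 1 protocol and not to the objectives of the feasibility study. The primary pain outcome is untouched. The size of any distortion in NRS points cannot be given, since the protocol states no acute effect size.

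The conclusion assumes that 6.6.1 is the operative list of scales, and that the pharmacokinetic figures in 4.1 apply to the study product. The 79% to 89% figure also assumes exponential decline from the peak. The qualitative conclusion does not depend on it, because 30 minutes is within the stated activity period in any case.

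**What to change.** Choose one of two repairs.

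1. **Keep anxiety as an effectiveness outcome.** Add an anxiety NRS at Day 0 before the first dose, in both 6.6.1 and Table 1-1; the additional efficacy row in that table is at present marked weekly only, so adding anxiety to the weekly list would not by itself create a baseline. Add anxiety to the weekly efficacy list, not tied to a session, with the same recall period as the other weekly scales, and continue it after treatment stops. State in 6.7.1 that the change from baseline uses only these scores. Keep the 30-minute score for tolerability and alerts.
2. **Treat anxiety as tolerability only.** Remove it from the effectiveness lists in the synopsis and 6.7.1, including the sentence on judging benefit, and report it with the other post-dose measures.

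Collecting the weekly item in controls is optional, given the disclaimer in the synopsis; it would be needed only if a comparison were wanted.

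The first repair costs one extra item at Day 0 and one a week in the ePRO, plus wording. The second costs wording only, and gives up any statement about benefit on anxiety. Since this protocol is to be resubmitted for ethical review, either change can go into that submission.
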